To minimize the AF-associated risk of stroke, international guidelines[9, 12] recommend providing oral anticoagulants (OACs), either vitamin K antagonist (VKA) or non-vitamin K antagonist oral anticoagulants (NOACs), to male patients with ≥ 1 and female patients with ≥ 2 of the following risk factors: congestive heart failure; hypertension; age ≥ 75 years; diabetes mellitus; prior stroke or transient ischemic stroke or thromboembolism; vascular disease; age 65 to 74 years and female sex (i.e., CHA₂DS₂-VASc score). Despite compelling evidence supporting the strong efficacy of OACs in preventing stroke in AF patients, the use of these agents is limited by three major factors: under-prescription, non-adherence, and a suboptimal therapeutic range for VKA treatment. A systematic review of 54 studies found that 50% of high-thromboembolic-risk AF patients did not receive appropriate OAC therapy.[13] Likewise, a recent study[14] of 9,727 patients with AF in Hong Kong reported that nearly 40% did not receive OAC therapy and another 40% received only conservative aspirin therapy, which has proven ineffective for AF-related stroke prevention. OAC under-prescription is mainly attributable to physicians' concerns regarding the side effect of an increased bleeding tendency,[15] as patients are more willing to bear this risk, given the benefit of preventing a stroke episode.[16] However, physicians inaccurately perceive that patients fear the risk of bleeding more than the risk of stroke.[17] The investigation team revealed similar findings in another local study,[18] where physicians reported the perception that patients were at a high risk of developing adverse events as the most common barrier to OAC prescription. The physicians reported moderately high levels of decisional conflict, as they did not fully understand patients' views regarding the risks and benefits of OAC use.[18] Such studies have shown that the inability of patients to effectively convey their values and preferences to physicians has contributed to the low OAC utilization rate among AF patients.

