This will be a sequential mixed-methods study with two phases. Phase 1 will comprise a prospective, single-blinded RCT to investigate the effects of the nurse-coordinated integrated care model on various health outcomes among patients with AF. Phase 2 will comprise an exploratory qualitative study to determine how and why the intervention works. Figure 1 outlines the Phase 1 study implementation protocol. After collecting baseline data, the research nurse (RA1) will randomly allocate patients into the intervention or control group. Block randomization (block size: 8, 10, or 12) will be used to ensure even participant distribution between the two groups. The block size

and respective study group allocation sequence will be determined using a computer-generated sequence. Chronologically recruited patients will be allocated to the study groups by RA1 according to this computer-generated sequence. Participants allocated to receive the nurse-coordinated integrated care model will be provided with an appointment 1–2 weeks before their next scheduled medical appointment to initiate the intervention. The participants allocated to the control group will continue to receive conventional care as arranged by the hospital. An independent research assistant (RA2) who is blinded to the study group allocations will collect post-intervention data through medical record reviews and telephone interviews upon completion of the intervention and 6 months thereafter.

Figure 1. Study implementation protocol

Study participants

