The proposed sample size was estimated based on the primary outcome of HRQoL. To our best knowledge, no previous study examined the effect of a nurse-coordinated empowerment-based care model on AF patients. However, we have identified a few similar interventional studies targeting patients with different diseases, including diabetes[42,

43] and hemodialysis recipients.[44] Of these studies, the effect sizes of the empowerment interventions on HRQoL ranged from 0.09 to 1.17, depending on the HRQoL domains. In general, an experimental design involving a larger sample size can enable researchers to detect a smaller effect size on an outcome at a specific statistical power and significance level. However, a small effect size may not be clinically important. Therefore, after considering both the clinical relevance and previous study findings, the sample size of this study was determined to yield adequate power for the detection of at least a small to medium effect size[45] on the primary outcome. Using power analysis software package PASS 13 (NCSS, Kaysville, USA), we estimated a sample size of 176 per study arm to yield 80% power at a 5% significance level for the detection of an effect size as small as 0.3 on our primary outcome when comparing the two study arms at the post-intervention time points. After allowing for a potential dropout rate of 10%, 392 participants (196 per arm) will be recruited.

[figure not shown]
For Phase 2 of the study, a purposive sample of 30 participants from the intervention group will be invited to participate in a qualitative interview. Participants with different treatment responses to the nurse-coordinated integrated AF care model will be recruited according to changes in their post-intervention HRQoL scores. Ten participants will be selected from each range of HRQoL changes: 0–34th percentile, 35th–68th percentile, and >68th percentile.

Study interventions

Intervention group: Nurse-coordinated integrated care model for AF

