<pre> graph TD A[Peer sharing & address concerns] --> B[Skill building] B --> C[Structured education] C --> D[Self-reflection & goal setting] D --> E[Action planning] E --> B </pre>	
 Be supportive to assist patients to identify their inadequacy in self-care Avoid judgmental attitudes Be patient-centered in identifying the barriers to self-care Use active listening to identify concerns, fears and beliefs that may hinder effective self-care Be collaborative with the patients to work through ambivalence to set patient-directed goals Use reflection and paraphrasing to validate patients' feelings and their capacities to solve problems Be respectful to the expertise of patients Genuinely believe in patients' ability to make the changes Acknowledge patients' right and responsibility to make self-care choices and to be the primary decision makers

3. Nurse-initiated telephone support

The nurse will provide continued support by telephone after the face-to-face sessions have been completed (two weekly and two bi-weekly calls). A telephone record containing patients' clinical profiles, AF-related treatments, self-management goals, and action plans will be used to facilitate the process. The nurse will monitor patients' adherence, symptom profiles, treatment efficacies, adverse effects, and goal attainment progress; identify barriers in the self-care process; and provide resolutions and continued support via the telephone. Health counseling and advice given will be documented to guide subsequent telephone correspondence.

4. Patient-initiated contact for professional advice

All participants from the intervention group will be provided with telephone access to the nurse for inquiries regarding disease management during office hours. The nurse will provide health advice and counseling accordingly. For severe undesirable symptoms and adverse reactions to medications, the nurse will attempt to advance patients' follow-up appointments or advise patients to seek emergency medical care if necessary. All correspondence and advice given will be documented in patients' profiles.

Control group: Conventional care

The control group will receive the conventional care provided by the study hospital.

Fidelity monitoring of the study intervention

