The 20-item AFEQT[50] measures disease-specific HRQoL in AF patients using 4 subscales: symptoms, daily activities, treatment concerns, and treatment satisfaction. All subscales are rated on a 7-point Likert scale, with higher scores indicating a poorer HRQoL. The subscales' Cronbach's alphas ranged from 0.88 to 0.95, the test-retest reliability and construct validity are satisfactory, and the instrument is responsive to treatment.[50] This investigation team developed the Chinese version of the AFEQT, which is currently undergoing psychometric validation.

Hospital Anxiety and Depression Scale (HADS, Chinese-Cantonese version)

The 14-item Chinese-Cantonese version of the HADS[51] will be used to measure anxiety and depression. This instrument is rated on a 4-point Likert scale, with higher scores indicating more intense anxiety and depression. The HADS is reported to have good internal consistency (Cronbach's alpha = 0.86) and satisfactory factorial, concurrent, and criterion validity.[51]

Data analysis

The statistical analysis of the outcome comparisons will be performed based on the intention-to-treat principle. Variables with skewed data will be transformed appropriately prior to analysis. Baseline characteristics between the two study arms will be compared using the t-test or chi-square test where appropriate. A mixed-effects model will be used to compare differential changes in the outcome variables over time and between the two arms. The mixed-effects model can account for intra-correlated repeated-measures data and produce unbiased estimates even if some data are missing, as long as the data are missing at random. All statistical analyses will be performed using SAS version 9.4 (SAS Institute, Cary, NC). All statistical tests will be 2-sided, with a significance level of 0.05.

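### No harm outcome is named for either arm, and adverse effects are monitored only inside the intervention, so benefits cannot be set beside comparably collected harm counts

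*Combined protocol and SAP*

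**What the plan says.** - **Population and purpose.** The eligibility criteria (Study participants) require that patients are not on OAC. The section on challenges in arrhythmia and risk factor control calls for a care model that optimises OAC prescription. The section Work done by us gives, as a reason for a more intensive approach, preliminary data that didactic education did not raise OAC use.
- **The recognised trade-off.** The background attributes under-prescription mainly to physicians' "concerns regarding the side effect of an increased bleeding tendency".
- **Where adverse effects appear.** Under Nurse-initiated telephone support, the nurse monitors adherence together with "symptom profiles, treatment efficacies, adverse effects, and goal attainment progress". Under Patient-initiated contact for professional advice, patients in the intervention group can telephone the nurse, and the text provides for severe symptoms and adverse reactions to medication.
- **Control arm.** "The control group will receive the conventional care provided by the study hospital." No event collection is described.
- **Outcomes and analysis.** Outcome measures lists decision compatibility, MMAS-8, AFEQT and HADS. Data analysis describes no safety analysis.
- **An existing route.** Under Study design, a research assistant (RA2) blinded to allocation will "collect post-intervention data through medical record reviews and telephone interviews", at the end of the intervention and 6 months later. The text does not say which items are taken from the records, and names no clinical events.

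**The concern.** Because nobody is on OAC at entry, every OAC start during the trial is new exposure to bleeding risk. If the programme works as hoped, that exposure may differ between arms. Yet nothing in the plan collects harms in the same way from both arms.

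Two things are at stake. First, a favourable finding on quality of life or OAC decisions would stand alone, with no comparably collected count of deaths, strokes or major bleeds beside it. Second, the only harm information the trial is described as generating comes from contacts that exist in one arm. If it were ever summarised by arm, the intervention would tend to look worse because someone asks there.

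The gap is also one of time. The four nurse calls (two weekly, two bi-weekly) span about 2×1 + 2×2 = 6 weeks of a 13-week programme. For the 6 months after the programme, no harm capture is described in either arm.

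**Working it through.** **1. The plan's own sample size.** The plan states "we estimated a sample size of 176 per study arm" for "80% power at a 5% significance level for the detection of an effect size as small as 0.3" on quality of life. Also, "All statistical tests will be 2-sided, with a significance level of 0.05".
- Normal approximation: n = 2(1.96 + 0.8416)² / 0.3² = 174.4, so 175 per arm.
- The t-test solution is 175.4, so 176 per arm. Power at 176 is 0.80.
- Dropout of 10%: 176 / 0.9 = 195.6, so 196 per arm, 392 in total.

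The figures reproduce. They are sized for quality of life and carry no information about harms.

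**2. Precision if harms were collected equally.** The documents give no event rates for this population, so the risks below are assumptions, cumulative over follow-up. With 196 per arm, the 95% half-width is 1.96 × √[p₁(1−p₁)/196 + p₂(1−p₂)/196].

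| Assumed risk, control v intervention | Expected events | Difference (points) | 95% half-width (points) |
|---|---|---|---|
| 1% v 2% | 2.0 v 3.9 | 1.0 | 1.96 × √(0.0295/196) = 2.4 |
| 2% v 4% | 3.9 v 7.8 | 2.0 | 1.96 × √(0.0580/196) = 3.4 |

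In both rows the half-width exceeds the assumed difference. With no events in an arm, the one-sided 95% upper limit is 1 − 0.05^(1/196) = 1.5%.

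**3. Power, by a second route.** Assumed annual rates are multiplied by 0.75 year (13 weeks plus 6 months, about 39 weeks). The test is two-sided 5% for two proportions, with pooled variance under the null and unpooled under the alternative.

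| Assumed annual rates, control v intervention | Expected events in 196 per arm | Power | n per arm for 80% power |
|---|---|---|---|
| Bleeding 1% v 2% | 1.5 v 2.9 | 10% | 3,104 |
| Bleeding 2% v 4% | 2.9 v 5.9 | 17% | 1,534 |
| Bleeding 3% v 6% | 4.4 v 8.8 | 23% | 1,011 |
| Stroke 4% v 2% | 5.9 v 2.9 | 17% | 1,534 |
| Stroke 5% v 2.5% | 7.4 v 3.7 | 20% | 1,220 |

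**4. Dilution.** These scenarios apply the doubling or halving to a whole arm. Under intention to treat, only the between-arm difference in OAC uptake contributes. As an illustration, assume a 2% risk without OAC, a doubling on OAC, no uptake in controls and a 30-point uptake difference. The intervention-arm risk is then 0.7 × 2% + 0.3 × 4% = 2.6%. The difference is 0.6 points against a half-width of 1.96 × √[(0.0196 + 0.0253)/196] = 3.0 points.

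**The case against.** The strongest reply is about scope. The stated aims are decision compatibility, adherence, anxiety, depression and quality of life. Physicians prescribe, the background cites guidelines recommending OAC for this risk group, and the nurse is to present risks and benefits even-handedly. A trial of a care model need not be a safety trial, and this one is far too small to be one. That explains why harms are not a powered outcome. It does not explain leaving them uncollected when a blinded record review is already planned in the trial.

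Several stronger readings are tempting, and the documents do not support them:

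- **That one-arm monitoring is why the trial cannot say whether bleeding rises or stroke falls.** Equal collection would not change that. The size and length of the trial settle it, as the working shows.
- **That a biased adverse-event table is planned.** None is. The call records serve care delivery, and the fidelity section files and codes contacts for coordination and checking against the intervention protocol. That section's closing remark that the data go forward for interpretation does not announce a between-arm harms comparison. The bias is a risk if those records are used that way.
- **That harms are excluded from RA2's review.** They are not named. The review items are not listed, and the content of Figure 1 is not shown.
- **That a record-based comparison would be free of bias.** Blinded, identical extraction removes differences in how records are read. It does not remove differences in who presents for care: the programme teaches symptom monitoring and crisis management, and the nurse may bring appointments forward or advise emergency attendance. Death and major stroke are little affected. Emergency visits and lesser bleeds are.

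**Conclusion.** The point stands as an omission that is cheap to repair. No harm outcome is named for either arm, and the only described monitoring of adverse effects belongs to the intervention.

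What a repair buys is limited: comparably collected, descriptive counts for oversight and honest reporting. Under the assumed risks, the difference would be known to within about ±2.4 to ±3.4 percentage points, with 10–23% power for a doubling of bleeding or a halving of stroke. All event rates are assumptions. The conclusion that precision is low holds across the range shown, and dilution through incomplete OAC uptake makes the detectable signal smaller still. A reader should not infer that the amended trial could establish a change in bleeding or stroke.

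**What to change.** Amend Outcome measures and Data analysis as follows.

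1. Add a fixed list to RA2's blinded record review, in both arms and at both post-intervention time points: death, stroke/TIA and major bleeding, each with a written definition.
2. Report counts and risk differences with 95% confidence intervals by randomised arm, labelled as descriptive safety data without hypothesis tests.
3. Keep events known only from nurse calls or patient-initiated contacts out of the between-arm comparison. They may be listed separately for the intervention arm.
4. If hospitalisations, emergency visits and lesser bleeds are also extracted, report them separately and state that the intervention may itself change care-seeking and detection.

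The cost is one extraction form, a short amendment and a few more minutes per record. It needs no extra staff, visits or patients. The main drawback is that the estimates will be imprecise, and the report should say so.

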The proposed study will be conducted at six medical out-patient clinics of the study hospital. We plan to use two approaches to recruit patients: 1) screening patients at the specialist out-patient clinics; and 2) identifying potential subjects from the Clinical Management System of the study hospital. All patients ≥ 65 years of age who attend the clinics will be invited to undergo rapid, single-lead ECG device-based screening for AF performed by trained student helpers. The study will arrange for patients with positive screening results to undergo a 12-lead ECG analysis onsite to confirm the diagnosis. The RA1 will check consecutive patients identified through this screening process against the following eligibility criteria for study participation: (1) age ≥ 65 years, (2) community-dwelling, (3) confirmed diagnosis of AF, (4) a CHA₂DS₂-VASc score of ≥ 1 in men and ≥ 2 in women, and (5) no use of OAC therapy. Patients with impaired communication or cognitive abilities (i.e., an Abbreviated Mental Test score ≤ 6) or severe co-existing medical conditions (e.g., terminal illness) that would hinder participation in research activities will be excluded. For the first approach, one of the co-investigators of this project ([name]) had adopted the same approach, which indicated that the newly identified AF was found in 1.5% on a single time-point screening, and additional 1.2% was detected in those screened on multiple time-points.[41] As such, approximately 25,000 patients need to be screened to achieve the target sample size. To safeguard an adequate sample is recruited, a second approach to screen patients who have already established the diagnosis will be identified from the Clinical Management System (CMS). The RA1 will identify potential participants who are under the care of specialist out-patient clinics of the study hospital from the CMS. Patients with documented AF who met the aforementioned criteria and are not receiving appropriate OACs for stroke prevention will be approached for further screening according to the selection criteria. This approach is supported by a study [14] which indicated a serious gap between empirical evidence and practice in the local setting: among 9,727 patients with AF in Hong Kong: nearly 40% did not receive any OAC and another 40% were conservatively put on aspirin.

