After the risk assessment, the nurse will conduct a face-to-face session in a small-group (6–8 patients/group) format to empower patients regarding decision-making and communication with physicians. This face-to-face approach was selected in accordance with literature suggesting it to be more effective than a written format.[46] Additionally, group teaching can promote peer learning and modeling. The session will begin with a structured educational session on AF and its complications, with emphasis placed on understanding the link between AF and ischemic stroke and the deleterious effects of rapid ventricular rates on cardiac function. The currently available and suitable OAC options (warfarin and NOACs) and their pros and cons (including the self-financed nature of novel OAC) as well as the rationales for rate and rhythm control will also be discussed. To assist patients with decision-making regarding OAC use, a patient decision aid developed by the National Institute of Health and Care Excellence[47] will be used. This aid organizes treatment options in an Option Grids format, wherein 10 frequently asked questions are presented vertically downwards with the options presented horizontally across the table. This format facilitates comparison and clarifies the options. Numeric and graphic formats with pictograms will be used to help patients understand the absolute and relative risks of a stroke when not using OACs or a major bleeding episode while using OACs. Patients’ individual risk profiles will be used to illustrate their stroke risks with and without OAC and their bleeding risk with OAC in a graphical format. The nurse will present the risk and benefit information in a fair and balanced manner.

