Another care component will engage patients in shared decision-making regarding OAC use by empowering them to better communicate their decisions to physicians during upcoming medical consultations. This component will highlight the key points of assertive communication, including asking questions, expressing concerns, and stating opinions and preferences regarding OACs for stroke prevention. The patients will be encouraged to generate a list of questions and concerns to propose to their physicians. To enhance patients’ confidence in their ability to maintain assertive communication in stressful situations, a series of scenario-based patient models in video format will be used to optimize the acquisition of skills for handling challenging encounters. A role-play-based rehearsal will be conducted to allow patients to practice their new skills and observe others’ behavior. The nurse will debrief patients to discuss their performance and provide feedback. Throughout the session, the nurse will adopt a supportive and non-judgmental attitude.

2. Empowerment-based group educational module

The same group of patients will attend an empowerment-based educational module beginning 1 week after their medical appointments. The module will comprise five weekly educational sessions covering the following major topics related to AF self-care: i) medication management, ii) symptom monitoring, iii) crisis management, iv) activities and exercise, and v) risk factor management to reduce risks of stroke and bleeding. The educational content of each session will comply with the recommendations of major practice guidelines for AF management.[9, 12]

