Multiple methods will be used to monitor the fidelity of the study interventions. Assessment and record forms will be used to document the care activities provided to patients during the sessions, telephone calls, and patient-initiated contacts. The nurse will file these assessment records to facilitate care coordination. Care activities will be coded, tracked, and checked against the intervention protocol. A standardized manual will be developed to guide the delivery of each group-based education session. Moreover, the PI will randomly select five groups in the intervention arm for monitoring. Face-to-face sessions will be videotaped after obtaining the participants' consent. Two research

fellows will review the tapes and complete a performance checklist after a briefing session by the PI. In addition, the nurse will document reflective notes after each session and hold monthly discussions with the investigation team. Participants' attendance will be recorded. All these data will be submitted for interpretation.

Outcome measures

The following instruments will be administered at baseline, upon completion of the intervention, and 6 months thereafter.

Compatibility between patient and physician decisions

Patients will be asked to indicate whether a decision regarding the choice of OAC was made before the consultation and, if yes, details of the choice.[48] The physician's prescription of any OACs will be monitored after the consultation. The nurse will confirm prescriptions with the patients and trace prescription record information in the Hospital Authority's Clinical Management System. The patients' choices and physicians' prescription decisions will be examined to determine compatibility.

8-item Morisky Medication Adherence Scale (MMAS-8)

The MMAS-8 will be used to assess self-reported medication adherence.[49] Each item measures a specific medication-taking behavior using a dichotomous (yes/no) response (Items 1–7) or a 5-point Likert scale (Item 8). The scores range from 0 to 8, with higher scores indicating better adherence. The Chinese version yields acceptable internal consistency (Cronbach's $\alpha = 0.77$), good test-retest reliability ($r = 0.88$), and construct validity.[49]

Atrial Fibrillation Effect on QualiTy-of-life (AFEQT) Questionnaire

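### The plan does not say how baseline enters the mixed model; a common baseline mean or baseline covariate is, in large samples, never less precise than a change contrast and needs no extra data

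*Combined protocol and SAP*

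**What the plan says.** The quantitative model is given in one sentence of the Data analysis section: "A mixed-effects model will be used to compare differential changes in the outcome variables over time and between the two arms." The section adds that the model handles correlated repeated measures and tolerates data missing at random. It does not say whether baseline is a response with its own mean in each arm, a response with one mean shared by the arms, or a covariate. It names no contrast, no primary visit and no covariance structure. The hypothesis under Research plan and methodology is also worded in terms of better changes in the scores.

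On timing, Study design says: "After collecting baseline data, the research nurse (RA1) will randomly allocate patients into the intervention or control group." Outcome measures says: "The following instruments will be administered at baseline, upon completion of the intervention, and 6 months thereafter."

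The sample size text under Study participants takes HRQoL as the primary outcome. It states 176 per arm for 80% power at the 5% level to detect "an effect size as small as 0.3 on our primary outcome when comparing the two study arms at the post-intervention time points". It then says: "After allowing for a potential dropout rate of 10%, 392 participants (196 per arm) will be recruited." It gives no baseline-to-follow-up correlation and does not say which SD the 0.3 is measured in.

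**The concern.** If the model gives each arm its own baseline mean, the treatment effect is the between-arm difference in change, and chance baseline differences between the arms are subtracted in full. Randomisation after the baseline visit makes that unnecessary. The expected baseline means are equal, provided allocation is made without foreknowledge of the sequence, and a model that uses this estimates the same treatment effect with a smaller, or at worst equal, large-sample variance.

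At stake is precision on the primary outcome that the baseline visit has already paid for. There is also a specification issue: several models with different standard errors fit the present sentence, and choosing one before the data are seen removes that freedom. Finally, the sample size text compares arms after the intervention while the analysis text compares changes, so it is unclear which contrast the 0.3 describes.

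**Working it through.** **Inputs from the documents.** Two-sided 5% level (Data analysis); effect size 0.3, 80% power, 176 per arm, 10% dropout, 196 per arm recruited (sample size text); baseline measured before allocation (Study design); instruments given at baseline and two follow-ups (Outcome measures).

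**Assumptions.** One follow-up visit, independent patients, equal SDs at baseline and follow-up, and a baseline-to-follow-up correlation rho of 0.3, 0.5, 0.7 or 0.88. The documents give no rho for HRQoL. The value 0.88 is the test-retest figure quoted for the MMAS-8, the only repeat-measure correlation in the documents; it serves here only as a high value.

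**The plan's own figure.** A two-sample t-test with d = 0.3 has 79.9% power at 175 per arm and 80.1% at 176, so 176 reproduces. 176/0.9 = 195.6, rounded up to 196 per arm, or 392. The same arithmetic fits a test on follow-up values or on change scores, so it does not show which was meant.

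**Variance per patient.** Let s0 and s1 be the baseline and follow-up SDs.

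- Change, free baseline means: s0² + s1² − 2·rho·s0·s1
- Common baseline mean or baseline covariate: (1 − rho²)·s1²
- Difference: s0² − 2·rho·s0·s1 + rho²·s1² = (s0 − rho·s1)², which cannot be negative

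With s0 = s1 = 1 these become 2(1 − rho) and 1 − rho², and their ratio is (1 + rho)/2. The covariate slope costs about one degree of freedom in 350.

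**Power at 176 per arm** (noncentral t, 350 df for change, 349 adjusted).

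Reading A, 0.3 in follow-up SD units: effective d = 0.3/√(2(1 − rho)) for change and 0.3/√(1 − rho²) adjusted. At rho 0.3 these are 0.3/√1.40 = 0.254 and 0.3/√0.91 = 0.314.

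Reading B, 0.3 in change SD units: effective d = 0.3 for change and 0.3·√(2/(1 + rho)) adjusted. At rho 0.3 the latter is 0.372.

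| rho | variance ratio | A: change | A: adjusted | B: change | B: adjusted |
|---|---|---|---|---|---|
| 0.3 | 0.65 | 66% | 84% | 80% | 94% |
| 0.5 | 0.75 | 80% | 90% | 80% | 90% |
| 0.7 | 0.85 | 95% | 98% | 80% | 86% |
| 0.88 | 0.94 | >99.9% | >99.9% | 80% | 82.5% |

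The standard error is smaller by 1 − √ratio: 19%, 13%, 8% and 3%.

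**With the planned dropout.** Take 196 baselines and 176 follow-ups per arm. A free-baseline mixed model has variance per arm (1 − rho²)/176 + (1 − rho)²/196; the common-baseline model has (1 − rho²)/176. At rho 0.3 this is 0.00517 + 0.00250 = 0.00767 against 0.00517, a ratio of 0.67. At 0.5 and 0.7 the ratios are 0.77 and 0.86. The extra baselines recover little of the difference.

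**The case against.** The strongest reply is that no error is shown. The sentence does not exclude a common baseline, and if the team already fits one, or uses baseline as a covariate, the gain is zero and the edit only adds clarity. This stands, and the point is put as an improvement.

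The size of the gain also rests on a correlation that the documents do not give. At rho 0.88 the standard error falls by only 3%. Unequal SDs change it too: at rho 0.7 the variance ratio is 0.98 if the follow-up SD is 1.25 times the baseline SD, and 0.63 if it is 0.8 times. This limits the size; the direction does not reverse in large samples.

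Equal expected baseline means depend on allocation without foreknowledge. The same research nurse checks eligibility and allocates from the sequence, and no concealment is described. The argument is therefore conditional on this.

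The calculation treats patients as independent, yet "the nurse will conduct a face-to-face session in a small-group (6–8 patients/group) format", and "The same group of patients will attend an empowerment-based educational module beginning 1 week after their medical appointments." Clustering by intervention group would alter the power figures and the standard errors of either model. No clustered power is given here because the proposed text contains no group term; that is a separate matter.

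A reader might infer from the 66% that the trial is underpowered. The documents do not support this: the figure needs rho 0.3, follow-up SD units for the 0.3, and free baseline means, none of which they state. A reader might also infer that the change contrast is biased. Under randomisation it is not; it is only less precise.

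**Conclusion.** The point holds as a no-cost improvement that should be made. The role of baseline is unstated, and a common baseline mean or baseline covariate is available from data already planned. In large samples its variance is never above that of the change contrast, and with equal SDs it is 65% to 94% of it for rho between 0.3 and 0.88. Adjusted power is at least as high under both readings of the 0.3. The advantage is material at low to moderate correlation; at 0.88 it is negligible under reading A and about 2 percentage points under reading B.

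This rests on allocation without foreknowledge, one follow-up, independent patients, equal SDs and assumed correlations. It shows neither a wrong sample size nor a shortfall from the stated 80%: the 176 and 392 reproduce, and what remains open is the contrast and SD to which the 0.3 belongs.

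**What to change.** Keep the existing sentence in Data analysis and add after it:

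> For the AFEQT score named as primary and for HADS anxiety and depression, the mixed model includes visit and arm-by-visit terms at the two follow-ups, with one common baseline mean for both arms and an unstructured covariance. The treatment effect is the between-arm difference with its 95% confidence interval at each follow-up, one of which is named as primary.

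The team must fill in which AFEQT score and which visit are primary. A near-equivalent is a mixed model of the post-baseline values with baseline-by-visit and arm-by-visit terms.

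Apply this to the MMAS-8, and to the AFEQT treatment concerns and treatment satisfaction subscales, only where a baseline score is meaningful. Eligibility requires "and (5) no use of OAC therapy", and some patients will be newly detected by screening. The binary compatibility outcome is not affected.

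In the sample size text, state which contrast, visit and SD the 0.3 refers to, and keep 392. Clustering by intervention group needs its own treatment; this text does not deal with it.

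The cost is two sentences in Data analysis and one clause in the sample size text, with no added patients, visits or data.
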